1.1 Synopsis

Title:	Technology and Family Thriving Study (Thrive)
Grant Number:	2 R42 AG063640-02
Study Description:	
Objectives*:	Primary Objective: To test the impact of different forms of technology (virtual reality vs. video chat) on quality of life and family relationships in older adults who reside in senior living communities and an adult child who lives at a distance. The study will also investigate whether responses to the technology and quality of life outcomes depend on older adults' level of cognitive impairment (MCI/ADRD).
Endpoints*:	Primary Endpoint: Quality of life, thriving, mental health, loneliness, family relationships, caregiver guilt Secondary Endpoints: Social, emotional, physical engagement during technology sessions
Study Population:	Older adults (age 50+) with mild cognitive impairments (MCI) or mild to moderate Alzheimer's Disease or related dementias (ADRD) who reside in senior living communities and an adult child who lives at a distance.
Phase* or Stage:	Phase II
Description of Sites/Facilities Enrolling Participants:	Senior living communities in two regions of the U.S.
Description of Study Intervention/Experimental Manipulation:	Dyads (older adult + adult child) will be randomly assigned to participate together in 4 weekly technology sessions using either (a) Virtual Reality (treatment) or (b) Video Chat (active control).
Study Duration*:	Approximately 4 months
Participant Duration:	Approximately 4 months

1.2 Schema

Note: Because participation in the intervention required both members of the dyad, if one member chose to withdraw during the intervention phase, the entire dyad was discontinued. However, after the

[figure not shown]
intervention phase was completed, individual members could withdraw independently, allowing the other member to continue participating in post-intervention and follow-up surveys. **Attrition prior to the end of the intervention phase:** 20 dyads + 2 individuals (out of 372 consented) = **42/372**, or **11.3%**. **Total attrition over the course of the trial:** 20 dyads + 12 individuals = **52/372**, or **13.9%**.

Participant retention was monitored throughout the study, and reasons for attrition were recorded. Attrition was categorized into the following predefined groups: (1) **Withdrew consent** (participants voluntarily discontinued for personal reasons, such as time burden or loss of interest); (2) **Adverse events** (participants discontinued due to health or safety reasons – physical or psychological – including withdrawal by the study investigator); (3) **Health-related limitations** unrelated to the intervention that prevented continued participation (e.g., hospitalization, fall, cancer treatment); (4) **Protocol deviations or ineligibility** identified post-randomization (e.g., undisclosed history of seizure); (5) **Partner withdrawal**, where the dyadic nature of the study required discontinuation when a study partner withdrew; (6) **Death** during the study period unrelated to the intervention; and (7) **Lost to follow-up**, where participants became unreachable and did not complete one or more follow-up assessments.

Participants who missed one or more survey assessments but later completed subsequent surveys were classified as having **intermittent missing** data. These cases were not considered lost to follow-up and were retained in all analyses for which valid data were available. Reasons for missed assessments were not always reported but were presumed to reflect temporary nonresponse rather than formal withdrawal or disengagement from the study. In addition, in rare cases, survey data were lost due to administrative or technical errors despite participant completion. These cases were treated as **missing (administrative)** in the relevant analyses.

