9.3 Populations for Analyses

Participants will be older adults with mild cognitive impairments (MCI) or mild to moderate Alzheimer's Disease or related dementias (ADRД) who reside in senior living communities and an adult child who lives at a distance. Dyads will be randomly assigned to one of two treatment conditions (video chat vs. virtual reality). All participants who are enrolled in the study and complete the baseline assessment will be included in the primary analyses regardless of whether they complete all components of the intervention.

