9.4 Statistical Analyses

9.4.1 General Approach

Primary analyses will be based on an **Intent-to-Treat (ITT)** approach in which all randomized participants will be analyzed according to their assigned treatment group, regardless of completion of the intervention. Primary analyses will be performed on the ITT population using appropriate statistical models to compare treatment groups. Secondary analyses will evaluate additional outcomes and mediation models to explore potential explanatory pathways. Missing data will be handled using appropriate statistical techniques including linear models with maximum likelihood estimation. Additional exploratory analyses may be conducted to explore trends, identify potential moderator variables, and generate hypotheses for future research. These results will be interpreted cautiously. All analyses will be performed using validated statistical software (SPSS, R, and Mplus), and findings will be reported in accordance with CONSORT guidelines and relevant best practices in the field. Where appropriate, adjustments for multiple comparisons will be applied to control for Type I error inflation.

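### A partner who did not ask to leave is not followed after the intervention when the other dyad member withdraws during it, although only the sessions need both members

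*Combined protocol and SAP*

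**What the plan says.** Section 1.2 (Schema) gives the rule: "if one member chose to withdraw during the intervention phase, the entire dyad was discontinued". The reason offered is that taking part in the intervention requires both members. Once the intervention phase is over the rule changes: "individual members could withdraw independently, allowing the other member to continue participating in post-intervention and follow-up surveys". Partner withdrawal is one of the predefined attrition reasons, described as the case "where the dyadic nature of the study required discontinuation when a study partner withdrew". The same section counts "20 dyads + 2 individuals (out of 372 consented") as lost before the end of the intervention phase, and "20 dyads + 12 individuals" as lost over the whole trial.

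The analysis sections point another way. Section 9.4.1 says that "all randomized participants will be analyzed according to their assigned treatment group, regardless of completion of the intervention". Section 9.3 says that enrolled participants with a baseline assessment "will be included in the primary analyses regardless of whether they complete all components of the intervention". On missing data, 9.4.1 says: "Missing data will be handled using appropriate statistical techniques including linear models with maximum likelihood estimation". It names no sensitivity analysis.

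Section 7.2 lists the reasons for which an investigator may discontinue a participant; a partner's withdrawal is not among them. Section 7.1 keeps the remaining procedures going for a participant who moves to a tablet after an adverse reaction to VR. It says nothing of a partner left behind when the other member withdraws.

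**The concern.** That the sessions need two people is a reason to stop the sessions. It is not a reason to stop surveying the person who remains. Section 5.5 has follow-up surveys done in person with residents and online with adult children, so neither depends on the other. Section 1.2 itself accepts follow-up of one member alone once the intervention phase has ended.

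What is at stake is missing outcome data in people who did not ask to leave. The loss is triggered by the other member's burden, health or reaction, and that could differ between VR and Zoom: section 2.3.1 lists dizziness, nausea and headset irritation as VR risks, and section 4.2 acknowledges differences in ease of use for the family member. Where residents and adult children are modelled apart, the experience that led to the partner's loss lies outside the model, which makes missing at random harder to defend. No other approach to missing data is specified.

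**Working it through.** **Inputs.** From section 1.2: 372 people consented (372/2 = 186 dyads); 20 dyads and 2 individuals lost before the end of the intervention; 20 dyads and 12 individuals lost in total. From section 9.2: planned attrition of about 15%. From section 6.1.2: all primary outcomes are asked at four key time points, namely baseline and 1 week, 1 month and 3 months after the intervention. The last three are T6, T7 and T8 in the numbering of sections 1.3 and 4.4. Not given: w, the number of the 20 dyads that held one member willing and able to continue surveys. It is taken as 0 to 20.

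**Step 1: the plan's own figures.**
- Before the end of the intervention: (2 × 20 + 2)/372 = 42/372 = 11.3%, as stated.
- Total: (2 × 20 + 12)/372 = 52/372 = 13.98%, which rounds to 14.0%. The stated 13.9% is truncated; nothing depends on it.

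**Step 2: the share tied to whole-dyad losses.** The 20 dyads are 20/186 = 10.8% of consented dyads and supply 40/52 = 77% of all individual losses. At most one person per dyad is lost only because of the rule, so at most 20/52 = 38% of losses, or 20/372 = 5.4% of those consented.

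**Step 3: attrition if willing partners had stayed.** Loss before the end of the intervention is (42 − w)/372; total loss is (52 − w)/372.

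| w | Before end of intervention | Total |
|---|---|---|
| 0 | 42/372 = 11.3% | 52/372 = 14.0% |
| 10 | 32/372 = 8.6% | 42/372 = 11.3% |
| 20 | 22/372 = 5.9% | 32/372 = 8.6% |

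The total column assumes that each retained partner stays to T8. The bottom row also assumes that in all 20 dyads exactly one member wanted to leave.

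**Step 4: what is missing for each such partner.** Three of the four key time points fall after the intervention, so at most 3 × 20 = 60 surveys are involved. Baseline, and any weekly surveys done before the dyad stopped, remain available.

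**Step 5: would one member's data be usable?** Section 9.4.2 says that for some analyses, with Aims 1 and 2 as examples, the dyad is not estimated together. One member's T6–T8 data can serve those models. They do not serve the dyadic models, or H2b, which needs engagement from both parent and child.

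**Step 6: does the count fit the rule?** Two individuals are counted as lost before the end of the intervention without their partners. Under the rule as written, a withdrawal in that phase removes both members. Either some partners did continue alone, or these two losses were of another kind; the section does not say.

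**The case against.** The strongest reply is that the effect may be small and that several larger claims a reader might infer are not supported.

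- *That outcome data are thrown away.* They are not. Sections 9.3 and 9.4.1 keep people with a baseline in the analysis. The post-intervention data are never collected.
- *That 20 willing people were lost.* The documents do not say so. Some dyads may have left jointly or been found ineligible. The denominator is people who consented, and formal consent precedes baseline (10.1.1.2), so some dyads may have left before baseline and fall outside the primary set. The flow figure is not shown and may give reasons.
- *That each member's consent is wholly separate.* Section 10.1.1.2 has the adult child, and the legal guardian if different, also consent for a resident with dementia. Half the residents are planned to have dementia (5.5). Whether that permission survives the adult child's own withdrawal is not stated.
- *That every analysis could use a lone partner.* Section 9.4.2 limits separate modelling to some analyses.
- *That the arms lost partners unequally.* The text gives no attrition by arm, and section 7.1 partly mitigates the most VR-specific trigger with the tablet option.
- *That power has suffered.* Counted per person, 14.0% is below the planned 15%.

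All of this stands, and it limits the size of the point. It does not supply a reason for ending the surveys, and no section restores T6–T8 follow-up for these partners. Section 1.2 is also written in the past tense with attrition counts, so follow-up may have closed. That affects which remedy is still open.

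**Conclusion.** The point holds as a matter of avoidable missing data and possible bias. The rule in section 1.2 ends follow-up for a partner who did not ask to leave, for a reason that applies only to the sessions, in a trial whose primary analysis is meant to include people whether or not they complete the intervention. The number affected is unknown, from 0 to 20. With continued follow-up, total attrition would lie between 14.0% and 8.6%; the lower figure needs one willing partner in every discontinued dyad, valid consent for each, and completion to T8. The direction and size of any bias cannot be computed without losses by arm. Because the change is cheap, it is worth making even if few people are affected.

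**What to change.** 1. In sections 1.2 and 7.2, define stopping the sessions and leaving the study as separate events. When a dyad stops sessions, invite each member whose own consent remains valid to T6, T7 and T8, state the date from which those surveys are timed, and analyse them as randomised.
2. For residents with dementia, state whether the adult child's or guardian's permission continues after the adult child withdraws.
3. Reconcile the rule with the 2 individuals counted as lost before the end of the intervention without their partners.
4. If follow-up has closed, report partner-withdrawal losses by arm and add a sensitivity analysis that departs from missing at random for these cases.

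The cost is protocol and consent wording and up to three surveys for at most about 20 people. Some will decline, and lone-partner data do not help the dyadic models. Item 4 needs only data already held.

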1.3 Schedule of Activities

Timeline for the Thrive study

Schedule of Assessments for the Thrive Study

	Screen	Consent	Baseline (T1)	Tech 1 (T2)	Tech 2 (T3)	Tech 3 (T4)	Tech 4 (T5)	Post-study (T6)	1 Mo (T7)	3 Mo (T8)
Eligibility	X									
Randomization		X								
Informed Consent		X								
Demographics		X								
Outcome Evaluations*										
Technology sessions - Positive Engagement (self-report)				X	X	X	X			
Technology sessions - Positive engagement (behavioral coding)				X	X	X	X			
Quality of Life			X	X	X	X	X	X	X	X
Mental Health			X	X	X	X	X	X	X	X
Thriving			X					X	X	X
Loneliness and social connection			X	X	X	X	X	X	X	X
Caregiver Guilt			X	X	X	X	X	X	X	X
Family bonding			X	X	X	X	X	X	X	X

* The outcomes listed above refer to general constructs rather than specific measures. Most outcomes will be measured using more than one self-report and/or behavioral assessment.

2 Introduction

2.1 Study Rationale

By 2030, it is estimated that over 20% of U.S. residents will be age 60 or older¹. Since people are living longer, the number of people with Alzheimer's disease (AD) and Alzheimer's disease-related-dementias (ADRD) is expanding exponentially, affecting approximately 5.4 million Americans.² As noted in the strategic directions of the National Institute on Aging (NIA; Goal C), scientists have made remarkable breakthroughs in helping people live longer. But now, we need to ensure quality of life. Until cures for the dementias are discovered, new technologies and interventions that can reduce the stress and emotional burden of AD/ADRD for older adults and their family members (NIA's SBA-Approved SBIR/STTR Priority Topics) are imperative. Virtual reality (VR) is an innovative, noninvasive, drug-free, and increasingly affordable tool that can help older adults and their family members manage the anxiety, stress, and feelings of isolation associated with dementia, as well as promote thriving. In addition, adult children increasingly do not live near their parents and are managing dual career families of their own, making it incredibly difficult to provide care from a distance.¹ Research shows that adult children who

care for an elderly parent from a distance experience distress, anxiety, social impairments, and often feel like their caregiving is inadequate.³ These experiences are even more difficult when their loved one has dementia because of the relentless, heartbreaking loss of the person they used to know—the loss of memories, ability to learn, and identity. COVID-19 has exacerbated all of these feelings of anxiety, isolation, and desperation on the part of the older adults and their family members. Even if a vaccine for COVID-19 is discovered, the long-term health effects of prolonged social isolation and the crisis of loneliness will persist. Technologies are critically needed to combat these adverse effects.

Rendever, with its innovative virtual reality (VR) platform, provides a solution to the unprecedented challenges of residents' feelings of social isolation, enabling and enhancing social connections with family even when physical contact is not possible. Rendever's advanced communication and networking technology allows multiple people to travel in VR, co-view photos and videos, and engage in novel activities together, all while sharing stories in the process, even if they live in different parts of the world. Our Phase I data indicate that Rendever is safe, easy to use, and transformative for residents and family members. In the pages below, we outline the positive impact Rendever has on residents' *and* family members' mental and relational health. Our pilot data also demonstrate that residents with mild cognitive impairment (MCI) and mild to moderate dementia can safely use the VR and that they loved using it, regardless of their level of cognitive impairment. Given the strong evidence of the feasibility and technological merit of Rendever from Phase I, we are pursuing Phase II with the goal of continuing the research and improving the efficacy of the long-distance features of Rendever with residents with MCI and AD/ADRD and their family members who live at a distance. We will continue to refine and test ease of use and user satisfaction of Rendever (replicating Phase I), while expanding the scientific goals of the project by testing the immediate and longer-term impact of Rendever on the quality of life of residents and their adult children in a rigorous experimental design. We will also continue to investigate whether residents with varying levels of cognitive impairment respond in unique ways to the VR. This will be accomplished by building on the Phase 1 research design in several important ways: (1) expanding the sample to multiple senior living communities to test the impact of Rendever on a larger and more diverse population of residents, (2) adding an active control group (video chat via Zoom) to provide a rigorous experimental test of the impact of Rendever, and to rule out the possibility that any such benefits are simply due to contact with family, (3) adding a 1-month and 3-month follow-up to determine if the potential benefits of Rendever are sustained over time, and (4) expanding our outcome variables to include a broader array of quality of life indices and caregiver guilt so that we can test Rendever's potential to improve the lives of residents in senior living communities, *and* the adult children who are involved in their care.

Phase II: VR as a Relationship Maintenance Tool with Residents with Cognitive Impairments

Largely due to the lack of disease-changing treatments for AD/ADRD, there has been growing interest in nonpharmacological interventions that can reduce the burden of dementia.⁴ Some of these interventions have been shown in meta-analyses to be quite effective. Interventions that rely on music therapies, exercise, reminiscence therapies, sensory stimulation, cognitive/emotional stimulation, behavior management, and person-centered care have been associated with a reduction in agitation, enhanced mood, and improved quality of life for residents with MCI and dementia.^{5 6 7 8} A key question is: what does VR offer beyond what is already available in these existing approaches?

In this project, VR is viewed as a relationship maintenance mechanism that promotes positive engagement. We conceptualize positive engagement as emotional connections between the resident and adult child, engagement in conversations with each other while in the VR, engagement in the technology itself, and positive affect (e.g., joy, excitement).⁹ We rely on some of the tenants of the

theory of resilience and relational load (TRRL) to explain why VR, as a relationship maintenance tool, fosters positive engagement. As the TRRL and other theories (e.g., attachment theory) suggest, people want to feel loved, secure, and valued.^{10 11} These feelings occur across the lifespan, but are especially salient at the end of life when one's social networks shrink and health is more easily compromised than at other points in adulthood.¹² The TRRL builds on the theory of emotional capital¹³ and argues that investing in one's relationships over time through positive relationship maintenance builds emotional reserves that people can draw from when they are stressed, promoting resilience and potential thriving. Positive relationship maintenance involves the "prosocial, strategic, and routine or habituated experiences, behaviors and actions people use" to sustain their relationships. Shared experiences in VR are prosocial maintenance activities that could help strengthen resident-adult child bonds and feelings of unification against life's challenges. When family members actively maintain their relationships, they also tend to communicate in more secure, engaged, supportive, and empathetic ways.¹⁹ Ultimately, these security-oriented stress appraisals, emotional connections, and communication are important because research has linked bonds with family and leisure activities to better mental and physical health in older adulthood.¹⁴ .

Virtual reality, however, is more than a pleasurable activity for residents with cognitive impairments. It has the potential to alter the way they feel about their relationships and the world around them. VR "is an experiential interface in which the components of perception (visual, tactile, and kinesthetic) are the bases for interactivity, encouraging a sense of 'being there'—that is, the sensation of being actually inside the virtual environment."¹⁵ Residents in senior living communities are often separated from the rest of society socially and spatially. There is a consistent body of literature on telepresence and the use of an array of technologies (e.g., robots, video chat, smart homes, multi-sensory interactive windows) to combat older adults' loneliness.¹⁶ However, VR is different than these methods because of the immersion into a virtual world; rather than simply chatting with family via a large video screen, rich sensory stimuli can make residents feel as if they are actually inside the virtual world engaging in real activities with them.¹⁷ . The shared, novel experiences allow residents and family members to reduce boredom, break out of their routine, and savor shared adventures and meaningful moments in real time, regardless of geographical separation.¹⁸

Virtual worlds can also create a feeling of security for residents with dementia, who are anxious without their family, and for their adult children, who long for an emotional connection with the parent they used to know. Social presence is a "sense of being with another" in a virtual environment.¹⁹ It allows people to transcend their location in space and feel as if they are with each other psychologically. Virtual reality activates the psychological processes in the brain that become stimulated when people are focused on each other. A component of social presence is co-presence or "the degree to which the observer believes he/she is not alone and secluded, their level of peripheral or focal awareness of the other, and their sense that the other is peripherally or focally aware of them."¹⁸ Taking residents with dementia back in time through VR allows them to experience the joy of their past and allows the adult children to experience their parent's true presence.²⁰ .

The positive engagement that shared VR creates should, in turn, improve the quality of life of residents and their adult children. **For residents with and without cognitive impairments, quality of life means being able to maintain important family connections, have control over their lives, and feel as if their lives still have meaning.**²¹ . We are conceptualizing quality of life as general happiness with one's life and also low levels of social isolation/loneliness, positive mental health, and the ability to thrive. Rendever could be a crucial way to connect residents with their adult children, reducing social isolation and

improving the mental and relational health of everyone involved. Virtual reality allows older adults to continue to grow, experience new sensations, travel, and live life outside senior living communities. This may be especially true if VR allows residents with varying levels of cognitive impairment to connect to their past and do things they can no longer do because of cognitive and/or physical limitations. Because of the immersive nature of VR, Rendever should be more effective at promoting these processes compared to other means, such as video chat. In Phase II, we also want to show that using Rendever has a longer-term impact beyond the moments right after its use. Importantly, adult children who live in another state might not have as many opportunities to engage in activities with their parents compared to a sibling who lives nearby. Shared VR experiences can create common ground and give the dyad something exciting to talk about that is unique to that relationship, fostering a social bond in ways that last beyond the VR sessions. Therefore, our first aim and hypotheses are:

AIM1: Determine whether Rendever (vs. control) improves **quality of life** for residents and their adult children who live at a distance.

- **H1a:** Residents and adult children in the VR condition (vs. control) will show significantly **greater improvements in quality of life** (reductions in loneliness, improvements in mental health and thriving) both concurrently and over time (relative to baseline).
- **H1b:** The positive effects of the VR condition (vs. control) on residents' and adult children's **quality of life** will be **mediated by** (explained by) increases in **positive engagement** (positive affect, engagement with the technology and with the adult child while using it, emotional closeness with the adult child).

A second aim of Phase II is to continue to determine the level of cognitive impairment for which Rendever is most beneficial. Virtual reality has been used successfully with older adults with MCI and mild to moderate AD/ADR to enhance cognition, navigation, spatial orientation, attention, spatial memory, mobility, and balance. Research with residents with and without dementia suggests that VR is enjoyable and can induce positive affect. For instance, virtual environments have been found to increase joy and relaxation in residents and reduce anxiety and sadness.¹⁶ Researchers have also tested sustained attention while using VR, versus a paper version of the task, among residents with MCI and dementia. Residents, regardless of the level of cognitive impairment, found the VR enjoyable, reported high feelings of security and low levels of discomfort and anxiety, and preferred the VR over the paper condition. Interestingly, residents with greater apathy preferred the VR condition the most and reaped the greatest benefits. Virtual reality has also been used with older adults without cognitive impairments for reminiscence therapy and shown that the number of memories generated is greater with familiar than unfamiliar settings.²² Other researchers have found that VR can enhance autobiographical memory in older adults with MCI²³ and that VR can improve memory in older adults with MCI more than music therapy. **Little research, however, has examined the impact of VR on older adults' social well-being, particularly among residents with dementia. What has been missing from VR is sophisticated networking and livestreaming functions, which Rendever provides.** The ability for residents to travel back in time to their childhood home and other memorable places with their adult child while sharing stories together should facilitate positive engagement for both of them.

We already demonstrated in Phase I that Rendever can be used safely with residents with MCI and mild to moderate AD/ADR and that residents loved the experience, regardless of their level of cognitive impairment. Our Phase I results suggest that Rendever is beneficial for residents with MCI and mild to moderate dementia, especially if it involves reminiscence therapy. We also found in our automated and human coding that the higher the MMSE-2 score (or the less dementia), the more engaged the resident

was in the LifeStory VR session. However, residents with dementia reported being more immersed in the VR sessions than residents with MCI. It could be that as the dementia becomes increasingly severe, it is more likely to restrict residents' bodily movements. However, dementia might enable residents to become more immersed in another world than if they have MCI. These speculations need to be tested with a larger sample in Phase II. We also did not have a large enough sample to test for differences between the two groups for quality of life indices. Therefore, research questions are posed instead of hypotheses. Phase II extends the literature by examining whether the impact of VR on residents' quality of life depends on their level of cognitive impairment, primarily because of the level of engagement. Likewise, the adult child's quality of life might also improve because of jointly benefiting from engagement in the VR with one's parent. Finally, Rendever should produce greater engagement than video chat because of the shared immersion into an altered reality. Therefore, our second aim and research questions are:

AIM2: *Determine whether the positive effects of Rendever (vs. control) on residents' and their adult children's quality of life depends upon residents' level of cognitive impairment (MCI vs. mild to moderate AD/ADRD).*

- **RQ1:** Are the effects of the VR condition (vs. control) on **quality of life moderated** by residents' level of cognitive impairment (MCI vs. mild to moderate AD/ADRD) both concurrently and over time (relative to baseline)?
- **RQ2:** If the effects of the VR condition (vs. control) on **quality of life** are moderated by residents' level of cognitive impairment, are these differences **mediated** by (explained by) group differences in **positive engagement**?

Finally, having parents move into a senior living community can be stressful and anxiety-producing for adult children. We focus on residents of senior living communities and their adult children living at a distance because the distance can make it challenging to maintain their relationship and difficult for the adult children to feel like they have control over the quality of care provided for their parents. Adult children who cannot easily visit their parents and monitor their care often experience care-giver guilt. They feel guilty and anxious that their parent is in a senior living community and report dissatisfaction with information they receive about their parent's care.²⁴ Adult children's guilt, worry, and stress about their parent's safety and care has been exacerbated with COVID-19 because the disease can spread rapidly in these communities and put its entire population at risk. Adult children have also been unable to physically visit their parents because of the pandemic, further contributing to their existing anxiety and guilt. To improve the quality of life of the resident and ease the concerns of the adult child, it is essential that the senior living community involve the adult child in the parent's care and provide programming that allows residents to experience a high quality of life. The synergy that is created through the shared VR experiences should reduce caregiver guilt for the adult child not only because the child is engaged in the VR with their parent, but also because they see first-hand the positive effects that it has on their parent's engagement over time. Thus, our final aim and hypotheses are posed:

AIM3: *Determine whether Rendever (vs. control) reduces caregiver guilt for adult children who live at a distance, and whether these effects depend on the adult child's own response to the VR and their parent's response to the VR (a dyadic effect).*

- **H2a:** Adult children in the VR condition (vs. control) will show significantly **greater reductions in caregiver guilt** both concurrently and over time (relative to baseline).

H2b: The effects of the VR condition (vs. control) on **adult children' caregiver guilt** will be **moderated** by the adult child's own **positive engagement** and the parent's positive engagement, such that the beneficial effects of the VR condition will be amplified when positive engagement is higher (vs. lower) for self and parent (a dyadic effect)

